## Primary Outcome Variables

### Aim 1:

Primary Efficacy Outcome: Percent time spent in the target range of 70-180 mg/dL during 2 weeks on each diet.

Secondary Safety Outcomes: We will measure the percent time spent in the hypoglycemic (<54 mg/dL, <70 mg/dL) and hyperglycemic (>180 mg/dL, >250 mg/dL) ranges. We will also measure the average sensor glucose values, standard deviation, and coefficient of variation during each 2-week diet period. We will compare the proportion of days with elevated fasting beta-hydroxybutyrate levels ( $\geq 0.6$  mmol/L) during each diet period. Number of episodes of diabetic ketoacidosis and severe hypoglycemic events during each period (baseline, diet periods, and washout period) will also be reported.

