- **Risks of ketosis:** Risks of the very low carbohydrate diet include the development of elevated ketone levels. These will be monitored frequently in the outpatient setting and all supplies will be provided to participants. Participants will also be educated on warning signs of DKA and will be instructed to call the study team for any elevated ketone levels  $> 1$  mmol/L or if they have symptoms of ketosis (nausea, vomiting, headache). If a participant develops DKA, they will be withdrawn from the study. Hyperglycemic events will be classified as diabetic ketoacidosis (DKA) if all of the following are present:
  - Symptoms of polyuria, polydipsia, nausea, or vomiting;
  - Serum ketone level  $> 1.5$  mmol/L or large/moderate urine ketones;
  - Serum bicarbonate  $< 15$  or venous pH  $< 7.24$  or arterial pH  $< 7.3$ ;
  - Treatment provided in a healthcare facility;
- **Risk of loss of confidentiality:** As in any study, there is the potential for loss of confidentiality. Female subjects of childbearing potential will require urine pregnancy testing prior to enrollment in the protocol, and results of this testing have potential to result in loss of confidentiality.
- **Risk of glycemic deterioration:** It is possible that changing dietary requirements or insulin doses may result in glycemic deterioration. Likewise, adolescents may have glycemic deterioration due to non-compliance. During the study, dose adjustments will be made according to standard of care to prevent hypoglycemia and hyperglycemia.
- **Risk of CGM:** Participants have the option of using FDA approved CGM as part of clinical care in our clinics. There is a low risk of developing a local skin infection at the site of the sensor needle placement. Itchiness, redness, mild bleeding, and or bruising may occur at the insertion site. Subjects may develop localized reactions to adhesive used to secure the sensor.
- **Risk of study questionnaires:** Participants may experience some distress when discussing factors important to diabetes, diabetes management, and psychosocial stressors

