#### Minimizing Risks:

- **Risks of Very Low Carbohydrate Diet:** In order to minimize the symptoms associated with transitioning to a low carbohydrate diet abruptly, participants will be encouraged to stay hydrated to help them acclimate and avoid unwanted symptoms.
- **Hypoglycemia/Hyperglycemia:** Participants will be contacted frequently during the course of the study. Blood draws will be done frequently during the HRU/CSRJU/Masonicare admission to minimize hypoglycemia and hyperglycemia. Intravenous glucose will be available in case hypoglycemia occurs. All infusates containing insulin are prepared under a filtration cabinet (Laminated HLDA filter) by qualified personnel using sterile disposable materials.
- Participants will be encouraged to monitor closely for signs of glycemic deterioration and will be able to contact our diabetes staff at any time if concerns arise.
- At the end of each visit, the participant will receive guidance for glucose monitoring, food intake, and insulin dosing as needed.
- During the study, insulin doses will be adjusted regularly (2-3 times per week as needed) to prevent hypoglycemia. Participants will use a real-time CGM that will provide alerts at the time of hypoglycemia and allow for early detection of hypoglycemia as well. Participants will be trained on treatment of hypoglycemia and to contact the study team immediately in any case of severe hypoglycemia.
- If any participant has 2 episodes of severe hypoglycemia, they will be transitioned to a regular diet after the 2nd episode of severe hypoglycemia.
- **Stable isotopes:** Isotopes will be carefully monitored, administered and will be prepared in the investigational pharmacy to ensure proper technique. As noted in

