### 5.2 Outcome Variables

#### 5.2.1 Primary Outcome Variables

**Aim 1:** The primary efficacy outcome will be the time spent in the target range of 70-180 mg/dL during the second week on each diet. Secondary safety outcomes will include the time spent in the hypoglycemic (less than 54 mg/dL, less than 70 mg/dL) and hyperglycemic (greater than 180 mg/dL, greater than 250 mg/dL) ranges. We will also measure the average sensor glucose values, standard deviation, and coefficient of variation during the second week on each diet period. We will compare average and range of fasting beta-hydroxybutyrate levels during each diet period. Number of episodes of diabetic ketoacidosis and severe hypoglycemic events during each period (baseline, diet periods, and washout period) will also be reported.

**Aim 2:** The primary safety outcome will be the mean levels of glucagon produced in response to hypoglycemia after each diet will be measured using a 2-step hyperinsulinemic euglycemic-hypoglycemic clamp. These will be measured after 15, 30, 45, and 60 minutes of euglycemia and hypoglycemia. Secondary safety outcomes will include mean levels of other counterregulatory hormones (cortisol, epinephrine, norepinephrine), and beta-hydroxybutyrate that are produced in response to hypoglycemia during the clamp will be compared after each 2-week diet period. Fasting levels of glucagon, free fatty acids, beta-hydroxybutyrate and IGF-1 (measure of growth hormone secretion), prior to the clamp will be compared after each diet period. Secondary outcome measures will include hepatic glucose production and adipose tissue lipolysis, which will be measured using stable isotope infusions during the euglycemic and hypoglycemic portions of the clamp. We will compare differences in hepatic glucose production during each clamp between a standard and very low carbohydrate diet. Additionally, deuterated water will be utilized to differentially evaluate the contribution of gluconeogenesis and glycogenolysis to endogenous glucose production.

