### 6.3.6 End of Study and Follow-up

- Participants will be instructed to contact study staff and make them aware of any adverse events that occur during the study (severe hypoglycemia, diabetic ketoacidosis, etc). Information about adverse events will also be asked at each study follow up visit.
- Upon completion of the clamp procedures, participants will be instructed to monitor their glucose levels carefully and contact clinic staff if they note that

insulin adjustments are needed. Follow up appointments with a diabetes care provider will be recommended within 2 weeks of the end of the study. Their primary diabetes provider will also be contacted and made aware that they have completed the study.

- If participants withdraw from the study early, participants will be instructed to monitor their glucose levels carefully and contact clinic staff if they note that insulin adjustments are needed. Follow up appointments with a diabetes care provider will be recommended within 2 weeks of ending the study. Their primary diabetes provider will also be contacted and made aware that they have withdrawn from the study.
- Diabetes providers will be made aware of any adverse events that take place during the study or information that is considered medically necessary for their overall health. Participants will be made aware of any information that may be shared with their diabetes provider. There is no plan to share results with the primary diabetes providers unless something pertinent to their diabetes management occurs during the study.

**6.3.7 Removal of subjects:** Participants may be withdrawn if they are unable to follow the dietary requirements and study procedures, including keeping a diet journal, testing ketone levels, and wearing a CGM at least 75% of the time.

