## 6.5 Planned Analyses

### 6.5.1 Primary Objective Analysis

- **Statistical Analyses Aim 1:** The unadjusted between-diet-group comparison of the primary endpoint, percent time in the target range of 70-180 mg/dL during the 2nd week of each diet, will be performed using a two-sided paired t-test. The adjusted analysis will be performed using linear mixed effects (LME) modeling, with a random intercept for each subject, diet effect, and adjusting for a participant's age, BMI and duration of diabetes. The mean adjusted between diet-group difference in percent time in the target range will be reported, along with the surrounding 95% confidence intervals based on 500 bootstrapped samples (2.5th percentile and 97.5th percentile of the distribution). Secondary outcomes, including time spent with hypoglycemia (<54 mg/dL, <70 mg/dL) and hyperglycemia (>180 mg/dL, >250 mg/dL), average sensor glucose level, will be analyzed similarly to the primary outcome. The proportion of days with elevated fasting  $\beta$ -hydroxybutyrate levels ( $\geq 0.6$  mmol/L) during each diet period will be compared using paired-proportions z-test in the unadjusted analysis and using generalized linear mixed effects (GLMM) modeling (a random intercept, link=logit for the binary outcome yes/no elevated levels with Bernoulli distribution) with covariates of age, BMI, and duration of diabetes. GLMM will also be utilized in the comparison of the number of episodes of diabetic ketoacidosis and severe hypoglycemic events during each period (a random intercept, link=log for a count outcome with Poisson distribution). Statistical analyses for all aims will be implemented using R and SAS 9.4 (Cary, NC) statistical software. Statistical significance will be established at the two-sided alpha of 0.05.

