#### 6.5.5 Interim Analysis (if applicable) – N/A

#### 6.5.6 Health economic evaluation – N/A

#### 6.5.7 Other - N/A

6.5.8 **Subsets and Covariates** - confounding variables include of age, BMI, and duration of diabetes. Details of the plan to evaluate confounding variables are above in Statistical Aim 1.

6.5.9 **Handling of Missing Data** – Participants that are unable to wear their CGM for at least 75% of the time will be excluded from the analysis.

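### Time below 54 and 70 mg/dL is a safety outcome, but the plan most naturally compares it on week 2 of each diet only, which leaves out week 1 and the on-diet exposure of anyone who stops a diet in its first week

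*Combined protocol and SAP*

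**What the plan says.** **Method.** Section 6.5.1 compares percent time in range during the second week of each diet by a two-sided paired t-test, with a linear mixed model as the adjusted analysis. Time below 54 and 70 mg/dL is in the list of secondary outcomes that closes with "average sensor glucose level, will be analyzed similarly to the primary outcome".

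**Window.** Section 5.2.1 agrees with 6.5.1: "The primary efficacy outcome will be the time spent in the target range of 70-180 mg/dL during the second week on each diet". The synopsis differs: "Percent time spent in the target range of 70-180 mg/dL during 2 weeks on each diet". The 6.2.1 table follows the synopsis. No section states a window for time below range itself.

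**Ways to stop a diet early.**
- Section 3.2.1, on ketosis: "If a participant develops DKA, they will be withdrawn from the study".
- Section 3.2.1, Minimizing Risks: "If any participant has 2 episodes of severe hypoglycemia, they will be transitioned to a regular diet". This takes effect after the second episode. The text does not say that the participant leaves the study.
- Section 6.3.7: "Participants may be withdrawn if they are unable to follow the dietary requirements and study procedures".

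**Missing data.** The only rule, in 6.5.9, is: "Participants that are unable to wear their CGM for at least 75% of the time will be excluded from the analysis".

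**Other safety data.** On severe events the synopsis says: "Number of episodes of diabetic ketoacidosis and severe hypoglycemic events during each period (baseline, diet periods, and washout period) will also be reported". Section 6.5.1 compares these counts by period with a Poisson mixed model and compares elevated-ketone days by diet. Section 6.5.2 analyses Edinburgh symptom scores from each clamp. Diet-related symptoms are screened weekly (6.3.5, Follow Up Calls), adverse events are asked about at follow-up visits (6.3.6), and the investigator reviews adverse events after each participant finishes (7.12). Section 6.5.3 Safety is marked N/A.

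**The concern.** A week-2 window makes sense for efficacy, because it lets the diet and the insulin doses settle first. It suits a safety outcome less well. Under 6.3.5 (Visits 2 and 4), insulin is reduced by 10-20%, as clinically indicated, when the very low carbohydrate diet starts, in order to prevent hypoglycemia. Week 1 is therefore when the new dose is first tried, and a week-2 comparison does not show it for anyone, including those who finish.

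The paired test also needs a value on both diets. Two of the three stopping routes are triggered by a glucose or ketone event, so the people without a week-2 value may not be a random subset. The trial is meant to supply safety information on this diet in adolescents (section 3.2). A reader of the planned hypoglycemia comparison could not tell whose exposure is missing, or why.

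**Working it through.** **1. The plan's own sample-size figure.** Section 6.4.2 gives 16 analysed for 80% power at effect size 0.75, two-sided alpha 0.05, paired t-test, with 20 enrolled at 20% attrition. With 15 degrees of freedom and noncentrality 0.75 × √16 = 3.0, power is 80.06%, and 16 is the smallest n that reaches 80%. Then 16 / (1 − 0.20) = 20. Both figures reproduce. The plan therefore allows for 20 − 16 = 4 participants without a paired value, from any cause and at any time. Nothing in this point changes the sample size.

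**2. Days used.** Each diet lasts 14 days and week 2 is days 8 to 14, so the comparison uses 7/14 = 50% of the on-diet days.

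**3. What a stop on the diet leaves.** If the last on-diet day is t, the week-2 window holds max(0, t − 7) on-diet days. A report over all on-diet days holds up to t.

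| Last on-diet day t | On-diet days in week 2 | All on-diet days |
|---|---|---|
| 3 | 0 | up to 3 |
| 7 | 0 | up to 7 |
| 10 | 3 | up to 10 |
| 14 | 7 | up to 14 |

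For any t from 1 to 7, the stopped diet has no on-diet week-2 value. This follows from the window alone.

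**4. What each analysis then does.**
- *Paired t-test:* the participant is dropped.
- *Mixed model:* it can keep a week-2 value from the other diet if there is one, but it cannot recover glucose data from the stopped diet. Someone withdrawn in week 1 of the first diet contributes nothing.
- *Moved to a regular diet after a second severe episode:* CGM may continue, but the plan does not say whether those days count as test-diet days.

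**5. If the 2-week window governs.** The loss of week 1 disappears, and a stopped diet keeps some data. Someone withdrawn during the first diet still has no second-diet value and still leaves the paired test. The 75% wear rule may exclude more participants, but its time base is not stated.

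**6. By-diet summaries.** Four safety items have a stated comparison by period or diet: DKA, severe hypoglycemia, elevated-ketone days and clamp Edinburgh scores. Diet-related symptoms, other adverse events, and early stops with reasons have none. The investigator's review in 7.12 is oversight and is not described as split by diet.

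**The case against.** **The window is inferred.** In 6.5.1 the word for similar analysis could refer to method only, and in 5.2.1 the sentence on time below range carries no window. This stands in part: week 2 is the likelier reading of 6.5.1, but the documents conflict, and step 5 shows what remains if 2 weeks governs.

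**The serious events are already counted.** DKA and severe hypoglycemia are compared by period, with no stated restriction to completers unless the wear rule is applied to them. This stands. Those counts do not replace CGM time below range, which also captures lows that are not severe events.

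**An all-days report cannot rebuild a paired difference** for someone who never starts the second diet. This also stands, and is why the report belongs beside the week-2 estimate and should not replace it.

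A reader might infer three stronger points that the documents do not support:
- *That by-diet safety analysis is absent because 6.5.3 is N/A.* Outcomes labelled as safety are analysed in 6.5.1 and 6.5.2.
- *That a stop as late as day 12 leaves no usable value, because 5/7 = 71% is below 75%.* This assumes that the rule is applied to week 2 and that days after withdrawal count as non-wear. Someone who wore the CGM throughout their time on study could instead be at 100%.
- *That 4 of 20 diet starters would be lost.* The 20 are enrolled participants, randomization follows a 1 to 3 week baseline period, and the 20% attrition has no stated cause or timing.

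**Conclusion.** The point holds as a cheap improvement to the analysis of one safety outcome. On the likelier reading of 6.5.1, the comparison of time below 54 and 70 mg/dL uses half of the on-diet days, omits the first week after the insulin reduction, and has no on-diet value for a diet stopped on days 1 to 7. The wear rule may remove more, by an amount that depends on an unstated base.

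A reader might go further and conclude that the hypoglycemia result would be biased in favour of the very low carbohydrate diet, or put a number on the shift. The documents do not allow this. They give no rate of early stopping and no glucose data for those who stop, and people may stop for reasons unrelated to glucose. The size and direction of any bias cannot be computed. The primary comparison of time in range and its power are unaffected.

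**What to change.** 1. In 6.5.1, keep the week-2 estimate and state its window explicitly for time below range. Beside it, report time below 54 and 70 mg/dL from all CGM days actually on each diet, for everyone who started that diet. Do not apply the 75% exclusion to this report. Show the days each participant contributes, and do not count days after a move to a regular diet as test-diet days.
2. Alongside, list descriptively by diet period the early stops with reasons, the screened diet-related symptoms and other adverse events. Section 6.5.3 is a natural place for this.

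**Cost.** SAP wording, one added estimate and one descriptive listing. CGM is already reviewed twice a week (6.2.2), and symptoms and adverse events are already collected, so no new visits, calls or samples are needed. The downside is a little more analysis work and on-diet periods of unequal length, which the days-contributed column makes visible.

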Even for youth who are engaged in actively managing T1D, postprandial hyperglycemia continues to pose a challenge for many reasons, including, delayed insulin absorption and action compared to absorption of glucose from the gastrointestinal tract and dysregulated glucagon secretion after mixed meals (5). Moreover, postprandial glycemic changes can differ substantially depending on the macronutrient composition of the meal. Specifically, meals with reduced carbohydrate but increased fat and protein content will lessen immediate postprandial hyperglycemia (6). For many, being able to avoid carbohydrates and adhere to a very low carbohydrate diet may be easier than administering varying amounts of insulin for variable amounts of carbohydrate intake. Importantly, VLCDs have not been formally studied in adolescents and young adults with T1D. Observational data on children using a VLCD are also conflicting. A small case series of 6 children with T1D on a low carbohydrate diet showed deficits in anthropomorphic measurements and elevated lipids, though in some cases a caloric deficit was also reported(7). Conversely, a recent observational study of 131 children with T1D on a VLCD reported no significant change in height percentile or SDS after initiating the diet (8). Prior studies have explored use of low carbohydrate diets in T1D, but none have specifically monitored for ketosis. In those studies, it is likely that the lack of carbohydrate intake led to lower insulin needs, thus increasing lipolysis and ketogenesis, and levels of ketosis while on this type of diet (9). Thus, this study aims to evaluate the metabolic and neurological effects of hypoglycemia as they relate to the diet, which is a key concern from clinicians managing patients on this diet.

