### 6.2.2 Safety and Pregnancy-related policy

- Women of childbearing age will have a urine pregnancy test performed at the time of the screening/enrollment visit and the need for contraception for the entire duration of the study will be discussed. Additional urine pregnancy tests will take place the morning prior to each clamp visit (visit 3 and visit 5).
- Hematocrit levels will be tested prior to the clamp procedures (visit 3 and visit 5). Samples will be obtained with the minimum necessary blood volume. The point of care YSI glucose determinations require only 0.3 ml of blood per measurement. We will ensure that blood volume obtained does not exceed a maximum of 5cc/kg in pediatric participants and 550 ml in adult participants
- Continuous glucose monitoring data will be reviewed twice per week (or more frequently as needed) to ensure participants are wearing the devices and to monitor for hyperglycemia and hypoglycemia. Insulin doses will be titrated by trained research staff based on clinical care standards to ensure safety by minimizing hypo- and hyperglycemia.
- Daily fasting blood ketone checks will be performed during the study intervention and as needed for symptoms of ketosis. If ketones are elevated, participants will be instructed to call the diabetes emergency line 24/7 for further instruction. All patients in our clinics are instructed to call this number if they develop elevated ketones at home. These values will also be reviewed 3 times per week when 24-hour dietary recall is performed.

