**Visit 2 Randomization (virtual/telephone or in person):**

- Anthropomorphic measures (weight, % body fat, % muscle mass, % water, % bone) – home or on scale in office.
- Insulin pumps and CGMs will be downloaded to assess glycemic control. The diabetes treatment regimen will be adjusted as clinically indicated.
  - If participants are starting the very low carbohydrate diet, insulin doses will be reduced by 10-20%, as clinically indicated, to prevent hypoglycemia.
- First diet will be assigned.
  - If participants are starting the very low carbohydrate diet, meals can be picked up 2-3 times per week at the metabolic kitchen located at Yale New Haven Hospital by study participants or by research staff. Research staff will work with participants to deliver the meals if they are unable to pick them up.
  - If we are unable to acquire meals from the metabolic kitchen, we will use a mail order meal service that provides information about macronutrient content of all meals provided that meet the standards of the dietary measures.
- Participants will be instructed to check daily fasting blood ketone levels.
- Participants will receive dietary instruction and review the dietary requirements of the study. Participants will be instructed to keep a dietary record (MyFitnessPal application, written, and/or with photos) for the duration of the dietary period.
- Participants will be instructed to call the pediatric diabetes emergency line (available 24/7) in any case of severe low blood sugar, elevated ketone levels, or symptoms of ketosis. Participants will also receive education on the treatment of hypoglycemia, we will ensure that all participants have glucagon at home.
- Participants will be contacted 3 times per week (2 scheduled, 1 unscheduled) for a 24-hour dietary recall. During these telephone follow up calls, food diary will be reviewed, ketone levels reviewed, and CGM data will be uploaded and reviewed.
- Prior to the HRU/CSRU/Masonicare admission, we will recommend a standard diet be given and no food be eaten after 9pm (except for in cases of hypoglycemia). Participants will be advised to limit exercise in the 3 days prior to study to limit acute effects of recent exercise on insulin sensitivity.

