### 6.5.2 Secondary Objectives Analyses

- **Statistical Analysis Aim 2:** Appropriate mathematical transformations (e.g., natural log or square root) will be applied to each outcome of interest, as necessary, to normalize the distribution. A paired t-test will be used in the unadjusted comparison of the primary outcome, mean levels of glucagon, during each diet period. LME will be used to model the trajectories of change in mean levels of glucagon over time (baseline, 15, 30, 45, 60 minutes) during each diet period and compared between diets. We will use the Likelihood Ratio Test (LRT, a mixture of two chi-square distributions with restricted maximum likelihood – RML - estimation) to select between an LME model with just a random intercept or an LME with a random intercept and slope. The mean response will be modeled using parametric (linear and polynomial effects of time) and semi-parametric (piece-wise linear or quadratic splines) effects of time, adjusting for participants' age, BMI, and duration of diabetes. The best model will be chosen based on its fit to the data (LRT for nested models and Akaike Information Criterion, AIC, for not-nested models).

Effect sizes will be reported as the between-diet differences with bootstrapped 95% CIs. Secondary outcomes of interest will also be modeled similarly.

- **Statistical Analysis Aim 3:** Using the validated Edinburgh Hypoglycemia Symptom questionnaire, participants will be asked to verbally rate their hypoglycemia symptoms on a 7-point Likert scale (lower scores indicate fewer symptoms) during the euglycemia and hypoglycemia portions of the clamp. In the unadjusted analyses, differences between euglycemic and hypoglycemic total scores on each diet will be compared using a paired t-test. Adjusted analyses will be based on LME, similar to the analyses described in Aims 1 and 2. In the secondary analysis, we will model mean hypoglycemia awareness score by domain (e.g., autonomic, neuroglycopenic, and malaise).

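### The Aim 1 ketosis model has a participant random intercept only, so its test and confidence interval are too optimistic if the diet's effect on ketosis differs between participants

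*Combined protocol and SAP*

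**What the plan says.** Section 6.2.2 sets the measurement: "Daily fasting blood ketone checks will be performed during the study intervention". Section 6.1.2 makes each diet two weeks long, so a complete participant contributes about 14 yes/no values per diet.

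Section 6.5.1 (Aim 1) gives two analyses of the proportion of days at or above 0.6 mmol/L. In the unadjusted one, the proportions "will be compared using paired-proportions z-test in the unadjusted analysis". The adjusted one is a generalized linear mixed model with "a random intercept, link=logit for the binary outcome yes/no elevated levels with Bernoulli distribution" and with age, BMI and diabetes duration as covariates. Significance is at two-sided 0.05.

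Earlier in the same section, the adjusted time-in-range difference gets "95% confidence intervals based on 500 bootstrapped samples" (percentile limits). Secondary outcomes, with CGM measures as the named examples, "will be analyzed similarly to the primary outcome". The ketone sentence comes next and names its own methods without mentioning a bootstrap. No section states what a bootstrap would resample.

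The ketone outcome is not the same throughout. It is the proportion of elevated days in the Synopsis and 6.5.1, the average and range in 5.2.1, and the average in 6.2.1.

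**The concern.** A participant random intercept makes a person's days on both diets alike. It assumes that the diet shifts everyone's log-odds of an elevated day by the same amount. The covariates are participant-level main effects, so they cannot absorb differences in that shift. If the shift does vary, the model treats some 14 days per diet as more information about the average diet effect than 16 people can supply. The standard error is then too small.

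The documents make variation plausible without giving it a size. At the start of the very low carbohydrate diet "insulin doses will be reduced by 10-20%, as clinically indicated, to prevent hypoglycemia", so the change in insulin differs between people. The background (2.2) ties "lower insulin needs, thus increasing lipolysis and ketogenesis" to this kind of diet.

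At stake is the stated precision of one secondary safety outcome. Too narrow an interval puts the upper limit for the increase in ketosis too low, and that is the limit a safety reader uses.

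**Working it through.** **1. The plan's own figure.** The plan states no power or precision for ketosis. Its Aim 1 sample size (6.4.2) reproduces: a paired t-test with n = 16, effect size 7.5/10 = 0.75 and two-sided 0.05 has noncentral-t power of 80.06%, and 16/(1 - 0.20) = 20 to enrol.

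**2. Inputs.** From the documents: 16 evaluable participants, 14 days, two diets, alpha 0.05. Assumed: intercept SD 1 logit; mean logit -1.4 (24-25% of days elevated); no covariates; SD τ of the diet effect (a participant's logit difference between diets) of 0, 0.5, 1.0 or 1.5.

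**3. Hand check.** The median model-based 95% interval in the null simulation has width 0.95, 0.94, 0.93 and 0.93 logits across the four SDs. So SE = width/3.92, and it does not grow with τ. Varying response adds roughly τ²/16 to the true variance. The rejection rate is then 2[1 - Φ(1.96 × SE/SD)], with SD = √(SE² + τ²/16).

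| τ | SE² | τ²/16 | SD/SE | Type I error |
|---|---|---|---|---|
| 0 | 0.0587 | 0 | 1.00 | 5.0% |
| 0.5 | 0.0575 | 0.0156 | 1.13 | 8.2% |
| 1.0 | 0.0563 | 0.0625 | 1.45 | 17.7% |
| 1.5 | 0.0563 | 0.1406 | 1.87 | 29.5% |

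**4. Simulation.** Data: logit = b0 + u_i ∓ d_i/2. The random-intercept logistic model is fitted by maximum likelihood. Type I error at b0 = -1.4:

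| Trials per setting | τ = 0 | 0.5 | 1.0 | 1.5 |
|---|---|---|---|---|
| 3,000 | 4.9% | 10.1% | 17.8% | 27.5% |
| 3,000 (separate run) | 4.6% | 7.6% | 16.9% | 27.0% |
| 1,200 | 5.4% | 8.1% | 19.6% | 28.6% |

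At τ = 0.5 the 10.1% is at the high end; the other runs and the hand check give about 8%. Other ketosis rates (3,000 trials each) show the same pattern: 5.0 / 8.5 / 13.7 / 23.0% with 11-12% of days elevated, and 4.5 / 9.8 / 19.7 / 30.2% with 50%.

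**5. Alternatives.**
- Paired t on each participant's difference in proportion: 3.5-5.7% in all twelve settings.
- Model with an added participant-by-diet effect (b0 = -1.4, 1,500 trials): 3.3 / 4.5 / 6.3 / 7.6% with a chi-square reference, and 2.0 / 3.1 / 4.7 / 5.5% with F(1,15). In a separate 300-trial run at b0 = -1 with t on 15 df, it raised 95% coverage from 81.0% to 94.3% at τ = 1.0 and from 71.3% to 94.7% at τ = 1.5.

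**6. Does the bootstrap repair the interval?** Coverage of nominal 95% intervals (bootstraps: 400 trials of 500 resamples, Monte Carlo error about 1.5 points; with the +1 logit effect, coverage is of the estimator's own long-run mean):

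| Interval | No effect, τ = 0 / 0.5 / 1.0 / 1.5 | Effect +1 logit |
|---|---|---|
| Model-based | 95 / 90 / 82 / 73% | 95 / 92 / 82 / 72% |
| Resampling participants | 93 / 92 / 91 / 93% | 91 / 90 / 90 / 91% |
| Resampling daily rows | 96 / 90 / 80 / 71% | 93 / 88 / 77 / 73% |

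Resampling rows corrects nothing. Resampling participants helps at τ of 1.0 or more, but falls short of 95% throughout and is worse than the planned model at τ = 0.

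**7. Event counts.** The Poisson model in 6.5.1 names no person-time. At equal weekly rates the diet-to-baseline count ratio is 14/7 = 2.0 for a one-week baseline and 14/21 = 0.67 for a three-week one. Between completed diet periods it is 14/14 = 1.0.

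**The case against.** The strongest reply is that the harm is hypothetical. The model is valid at τ = 0, no document gives τ, and individualized insulin changes do not show variation of a full logit. That stands, and it is why the size is stated only as a range.

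Second, type I error assumes no average effect, whereas the protocol expects ketones to rise, and over-rejection on a safety outcome errs toward caution. With an assumed standard-diet logit of -3 and a diet effect of +2, the planned model and the paired t both reject in 100% of trials up to τ = 1.0, and in 99.8% against 96% at τ = 1.5. So a large effect would be declared either way. The interval, however, is too narrow at any effect size once τ is appreciable.

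Third, the plan may already hold a sound test. The natural pair in the unadjusted comparison is the participant, and a z-test on participant differences had 6-8% error at every τ. A reader might infer that the z-test pairs days and ignores clustering. The text does not say so; it leaves the unit open, which is a matter of wording.

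Fourth, the list of outcomes treated like the primary one is introduced as non-exhaustive, so the bootstrap might extend to ketones. Even so, the unit is unstated and step 6 shows that it decides the result.

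Finally, a reader might infer that the plan gives Aim 2 a safeguard that it denies to ketones, because Aim 2 uses a likelihood ratio test "to select between an LME model with just a random intercept or an LME with a random intercept and slope". That slope is over clamp time, not over diet, so it is not a comparable protection.

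**Conclusion.** The concern holds conditionally. As written, the adjusted ketosis model has no term for differences between participants in response to diet. With 16 participants, 14 complete days per diet, intercept SD 1 and about 25% of days elevated, type I error is about 5%, 8-10%, 17-20% and 27-30% at diet-effect SDs of 0, 0.5, 1.0 and 1.5 logits. All but the first two of these inputs are assumptions.

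Three stronger readings are not supported. The planned model is not shown to be invalid, since it is correct if response is uniform. The trial's main conclusion is not in doubt, because the primary time-in-range test does not use this model. The plan's bootstrap is not a ready cure, on the coverage in step 6.

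The point also depends on which ketone outcome governs. If it is the average (6.2.1) or the average and range (5.2.1), the logistic model does not apply. That conflict is visible from the text alone and should be settled first.

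**What to change.** 1. Reconcile the ketone outcome across the Synopsis and 6.5.1, 5.2.1 and 6.2.1.
2. If the proportion of elevated days is kept, make the unadjusted test a paired t or signed-rank test on each participant's difference in proportion.
3. Add a participant-by-diet random effect to the adjusted model, with a small-sample reference distribution such as F or t on 15 df for 16 participants.
4. If a bootstrap interval is also reported, resample whole participants with both diet periods together, and label it supportive.
5. In the Poisson event model, add a log person-days offset, or report rates, wherever period lengths differ: the 1-3 week baseline or washout against a two-week diet, or a diet period cut short.
6. Limit the 75% CGM-wear exclusion in 6.5.9 to CGM endpoints. As worded it also removes ketone, event and clamp data. The documents do not allow the effect of this to be sized.

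The cost is SAP wording and minor programming, with no new data. If response varies, the ketosis interval widens and nominal power falls. For a +1 logit effect the paired t rejects in 98.6 / 95.3 / 77.6 / 55.1% of trials at the four SDs, against 99.5 / 98.6 / 95.0 / 88.9% for the planned model. Where τ is above zero, the planned model's higher figures come with its inflated type I error.
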